6.11.1.3.2 Tipping Point Analysis

If the primary efficacy analysis in Section 6.11.1.2 significantly favors NYX-2925, a tipping point sensitivity analysis⁴ for the primary efficacy endpoint will be conducted to investigate how severe

the departure from the MAR assumption data must be to overturn conclusion from the primary analysis.

In this analysis, the assumption will be that that missing data in the NYX-2925 group follows a MNAR pattern. A tipping point-based approach will be used such that the trajectories of the subjects in the NYX-2925 group after early withdrawal are assumed to be worse than placebo by a fixed amount (δ). The value of δ is the adjustment added during imputation to the change from baseline NRS scores at each visit after study discontinuation. This increment is added only to the imputed change from baseline NRS scores at visits after study discontinuation of the subjects in NYX-2925. The value of δ will increase in increments of 0.1 (i.e., 0.1, 0.2, 0.3) up to the point at which the treatment difference at Week 12 is no longer statistically significant. This analysis provides a measure of the degree by which the subjects in the NYX-2925 group who discontinued early would need to be worse at each post-discontinuation visit in order for the null hypothesis of no treatment difference to no longer be rejected. Each imputed dataset produced through PROC MI procedure will be processed as follows:

- All values imputed for the placebo group will remain unchanged
- All values imputed for the NYX-2925 group will be incremented by a value of δ, which will vary from 0 up to a value by which statistical significance is not reached
- The modified data will be analyzed using similar analysis as described in Section 6.11.1.

Results will then be combined using PROC MIANALYZE and will consequently be recorded.

The "tipping point" is defined as the value of δ at which the result changes from statistically significant treatment effect to a treatment effect that is no longer statistically significant. The larger the value of δ , the more robust the conclusion from the primary analysis, with respect to assumptions around missing data.

6.11.1.4 Supportive Analysis

6.11.1.4.1 Analysis of Covariance on change from baseline to Week 12 in the weekly mean of the NRS score assessing average pain intensity related to DPN in the past 24 hours

To assess the robustness of the result observed for the primary endpoint, an Analysis of Covariance (ANCOVA) model with site and treatment as factors, and baseline NRS score as a covariate will be employed as a supportive analysis.

[figure not shown]
The following is the sample SAS code that will be used to implement this analysis:

```
PROC MIXED DATA= DATAIN;
CLASS TREATMENT SITE;
MODEL CFB_WEEK12 = TREATMENT SITE BASELINE / SOLUTION;
LSMEANS TREATMENT / CL DIFF;
RUN;
```

The LS means, SEs, and 95% CIs will be provided for each treatment group, as well as treatment difference estimate, SE, and p-value at Week 12.

Page 36 of 57

6.11.2 Secondary Endpoints

All secondary endpoints will be analyzed using the mITT population. The secondary endpoints of this study are as follows:

6.11.2.1 Change from baseline in the weekly mean of the Daily Sleep Interference Scale (DSIS) scores at Week 12

A similar approach in modeling the REML-based MMRM as in the primary analysis will be applied to the change from baseline in the weekly mean of the DSIS scores at Week 12 except that the outcome variable will be change from baseline in the weekly mean of the DSIS scores at Weeks 1 through 12, and the fixed effects are as follows: site, treatment group, week, baseline DSIS score, and treatment-by-week interaction as terms in the model. Observed NRS scores at baseline and at each week, as well as the change from baseline NRS scores at each week will be presented by treatment group. The LS means, corresponding SEs, and 95% CIs for each treatment group will also be presented at each week. Additionally, the estimate, corresponding SE, and p-value of the treatment difference at Week 12 will also be presented.

Subgroup analyses as described in Section 6.11.1.5 may also be performed for this endpoint.

6.11.2.2 Percentage of subjects 'much improved' or 'very much improved' on the Patient Global Impression of Change by Visit

The number and percentage of subjects reporting each of the response levels will be summarized by treatment for Weeks 4, 8, and 12.

Analysis will utilize the Cochran-Mantel-Haenszel (CMH) test to compare the treatment groups, using the following SAS code:

```
PROC FREQ DATA=CMHDATA1;
TABLES TREATMENT*RESP / RISKDIFF CMH;
ODS OUTPUT RISKDIFFCOL2 = RISK CMH = CMH_PVAL;
RUN:
```

The number and percentage of subjects 'much improved' or 'very much improved' by treatment at each visit will be presented. The risk difference for NYX-2925 vs placebo, corresponding 95% CI and p-value for the CMH statistic also be provided by visit.

Summary statistics for the PGI-C as a continuous score will also be provided by treatment group at each visit. Scores will be analyzed using the same REML-based MMRM as in the primary analysis, except with the exclusion of a baseline covariate.

Observed scores at each week (4, 8, and 12) will be presented by treatment group. The LS means, corresponding SEs, and 95% CIs for each treatment group will be presented at each week along with the LS mean difference, corresponding SE, and p-value.

A listing of all PGI-C scores will also be provided.

6.11.2.3 Percentage of subjects achieving ≥30% and ≥50% reduction from baseline in the weekly mean NRS average pain intensity related to DPN at Week 12

Percentage of subjects achieving both $\geq 30\%$ and $\geq 50\%$ reduction from baseline in the weekly mean NRS average pain intensity related to DPN at Week 12 will be analyzed and presented as described in Section 6.11.2.2.

6.11.2.4 Change from baseline to Week 12 in Norfolk Quality of Life Questionnaire – Diabetic Neuropathy score

A similar approach in modeling the REML-based MMRM as in the primary analysis will be applied to the change from baseline to Week 12 in the QOL-DN total score except that the outcome variable will be change from baseline to Weeks 4 and 12 in the QOL-DN total score, and the fixed effects are as follows: site, treatment group, week, baseline QOL-DN total score, and treatment-by-week interaction as terms in the model.

Observed QOL-DN total scores at baseline and at each week (4 and 12), as well as the change from baseline QOL-DN total scores at each week (4 and 12) will be presented by treatment group. The LS means, corresponding SEs, and 95% CIs for each treatment group will also be presented at each week (4 and 12). Additionally, estimate, corresponding SE, and p-value of the treatment difference at Week 12 will also be presented.

Listing of the QOL-DN individual item scores, as well as the domain scores at baseline and at Weeks 4 and 12 will be presented.

6.11.2.5 Use of rescue medication, including the proportion of subjects using rescue medication, the frequency and amount used

The total number of tablets taken and percentage of rescue-free days per week will be summarized by treatment group.

The proportion of subjects that used rescue medication (one or more tablets) at any point after the first dose of study drug will also be summarized by treatment group. A Z-test on equality of two proportions will be performed to compare the treatment groups, using the following SAS code:

```
PROC FREQ DATA=DATIN ORDER=DATA;
    TABLES TREATMENT*RESPONDER / RISKDIFF(EQUAL VAR=NULL CL=WALD);
    ODS OUTPUT PDIFFCLS = DIFF PDIFFTEST = PVAL;
RUN;
```

A similar approach in modeling the REML-based MMRM as in the primary analysis will be applied to the weekly dosage of acetaminophen used except that the outcome variable will be the dosage of acetaminophen used at Weeks 1 through 12, and the fixed effects are as follows: study site, treatment group, week, and treatment-by-week interaction as terms in the model. The LS means, corresponding SEs, and 95% CIs for each treatment group will also be presented at each

week. Additionally, estimate, corresponding SE, and p-value of the treatment difference at each week will also be presented.

[figure not shown]
6.11.2.6 Cumulative response (percent reduction from baseline) in the weekly mean NRS average pain intensity at Week 12

[figure not shown]
A cumulative responder analysis will be conducted for the primary efficacy endpoint. in this analysis, response is defined as any percent reduction from baseline in the weekly mean NRS average pain intensity at Week 12. Subjects who do not achieve a reduction from baseline at Week 12, who have a missing result, or who prematurely discontinue from treatment prior to Week 12 will be defined as a non-responder (i.e., 0% reduction/improvement in percent reduction from baseline). A cumulative response curve will be generated in which the response level is on the x-axis (0-100%, in 10% intervals, with reference lines at 30% and 50%) while the associated cumulative proportion of subjects calculated for that response level (i.e., percent reduction from baseline) is on the y-axis. The difference in the cumulative response curves between treatment groups will be analyzed using a Kolmogorov-Smirnov test. This test determines if two samples of data are from the same distribution. The D statistic and associated p-value will be provided.

[figure not shown]
```
PROC NPAR1WAY DATA= DATAIN;
CLASS TREATMENT;
VAR RESP;
EXACT KS;
RUN;
```

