Subjects will be instructed to continue entering their average pain intensity, worst pain intensity, average pain upon walking, and usage of rescue medication over the past 24 hours into their study-issued handheld devices every night. Every morning upon awakening, subjects will complete the DSIS and confirm they have taken their study drug in the past 24 hours via their study-issued handheld device. Pain diary compliance will be reviewed at each study visit by the study staff, and reporting instructions will be reinforced. Subjects will be reminded of appropriate expectations around their participation in a clinical study and the importance of consistently and accurately reporting their pain intensity throughout the study. Each subject will undergo educational training on Accurate Pain Reporting (APR®) and Placebo Response Reduction (PRR®) via an electronic learning management system, aLearn® [Analgesic Solutions, Wayland, MA]. Review of these educational materials will be repeated for all subjects as refresher training This training is mandatory prior to randomization and at each site-based visit, with the exception of the final visit. An ongoing blinded data review (e.g., if pain score variability is increased on a subject or site level) will be conducted to monitor these metrics [Analgesic Solutions, Wayland, MA].

The following scales will be completed at the Baseline Visit (Visit 2): Brief Pain Inventory for Diabetic Peripheral Neuropathy (BPI-DPN), the Norfolk Quality of Life Questionnaire - Diabetic Neuropathy (QOL-DN), Patient Global Impression of Severity (PGI-S), Pain Catastrophizing Scale (PCS) and Sheehan – Suicidality Tracking Scale (S-STS).

The subject will be given a printed copy of the study specific S-STS to take home and complete during the Week 2/Visit 3 telephone or videoconference visit.

#### Treatment Period: Week 2/Visit 3

Subjects will be contacted by the clinic study staff via telephone or videoconference at the end of Week 2 (Visit 3) for assessment of compliance with study drug, rescue medication use and diary entries. The appropriate use of study drug and rescue medication will be assessed by subject interview. Subjects will be instructed to continue to take one capsule of study drug by mouth once daily throughout the study.

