For pain unrelated to DPN, subjects may use a nonsteroidal anti-inflammatory drug (NSAID) for up to two (2) days during a seven (7) day period. If the need for analgesics exceeds this period, the patient should call the Investigator to evaluate the cause of pain and the course of action. If a subject requires a NSAID for pain unrelated to DPN, the medication should be recorded as a concomitant medication and the adverse event must be recorded in the eCRF. Beginning at Week -1, DPN related pain intensity and rescue medication use will be recorded in the study-issued handheld device daily at bedtime. Subjects will enter their average pain intensity, worst pain intensity, average pain upon walking, and total rescue medication use during the past 24 hours. Pain intensity will be recorded using an 11-point NRS, with 0 being no pain and 10 being the worst pain imaginable. Every morning upon awakening, subjects will complete the Daily Sleep Interference Scale (DSIS) via their study-issued handheld device.

The following scales will be completed at the Screening Visit (Visit 1): MNSI, MDT, PGI-S and S-STS.

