# 7. SELECTION AND WITHDRAWAL OF SUBJECTS

### 7.1. Subject Inclusion Criteria

#### **Inclusion Criteria: Screening**

Subjects must meet ALL the following criteria to be enrolled in this study:

- 1. An Institutional Review Board (IRB) approved written informed consent and privacy language (Health Insurance Portability and Accountability Act (HIPAA)) authorization must be obtained from the subject prior to performing any study -related procedures.
- 2. Consent to being included in a research subject database.
- 3. Subject is  $\geq 18$  and  $\leq 75$  years of age.
- 4. Diagnosis of Type 2 Diabetes.
- 5. At least moderate pain intensity over the last week as assessed by PGI-S at Visit 1.
- 6. Hemoglobin A1c (HbA1c)  $\leq 11\%$  (measured at Visit 1).
- 7. Stable use of diabetic medications beginning 1 month prior to Visit 1 (adequate glycemic control with diet and exercise alone is also permitted).
- 8. Diabetic peripheral neuropathy, of symmetrical nature and in lower extremities for ≥4 years (DPN in the upper extremities is not exclusionary).

- 9. Presence of pain due to diabetic neuropathy for at least 6 months prior to screening.
- 10. Total score of  $\geq$ 4 on the Michigan Neuropathy Screening Instrument.
- 11. Body mass index  $\leq 40 \text{ kg/m}^2$ .
- 12. Absence of impaired hepatic function. Impaired hepatic function is characterized by a previous known diagnosis of chronic liver disease, and/or abnormal serum total bilirubin (TBL), or alanine transaminase (ALT), aspartate transaminase (AST), or alkaline phosphatase (ALP)>1.5x upper limit of normal (ULN) at screening.
- 13. Calculated creatinine clearance  $\geq 60$  mL/minute (Cockcroft-Gault formula).
- 14. Fasting triglycerides  $\leq 600 \text{ mg/dL}$ .
- 15. Except as noted in criteria 12-14 above, clinical laboratory values must be within normal limits, or deemed not clinically significant by the Investigator.
- 16. Female subjects of child bearing potential with a negative pregnancy test prior to entry into the study and who are practicing a highly effective method of birth control (e.g., oral or parenteral contraceptives, intrauterine device, barrier [condom and spermicide], abstinence) and who do not plan to become pregnant, breastfeed, or donate ova during the course of the study and for 28 days after the final administration of investigational product.

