For the primary efficacy endpoint, the weekly mean of the daily average pain intensity NRS score from the handheld device will be averaged for baseline after randomization. Change from baseline will be assessed for treatment group differences using a mixed model for repeated measures (MMRM) with factors for study site, treatment, week, treatment--by-week interaction, and including the baseline value of the response variable as a covariate. Line plots displaying the mean weekly NRS scores from Weeks 1 through 12 for each treatment group will be generated. In these plots, the horizontal axis will reflect the study week and the vertical axis will reflect the average pain score.

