6.11.1.2 Primary Efficacy Analysis

A restricted maximum likelihood (REML)-based mixed model for repeated measures (MMRM) will be utilized to analyze the change from baseline to Week 12 in the weekly mean of the NRS score assessing average pain intensity related to DPN in the past 24 hours.

The MMRM model will have site, treatment group, week, baseline NRS score, and treatment-by-week interaction as terms in the model. The unstructured covariance (UN) will be utilized as the within-subject covariance structure in the event that the model fails to converge using the UN, the covariance structure among Toeplitz (TOEP), first-order autoregressive [AR(1)], and compound symmetry (CS) for which the model converges and yields the least corrected Akaike's information criterion (AICC) will be used. The Kenward-Roger degrees of freedom correction will also be used for this analysis.

The estimate of the treatment difference at Week 12 and standard error (SE) will be derived from this model. Observed NRS scores at baseline and at each week, as well as their change from baseline at each week will be presented by treatment group. The LS means, corresponding SEs, and 95% CI for each treatment group, as well as the estimate, corresponding SE, and p-value of the treatment difference in LS means at each week will be presented.

The following is the sample SAS code that will be used for this analysis:

```
PROC MIXED DATA= DATAIN;

CLASS USUBJID TREATMENT WEEK SITE;

MODEL CFB = TREATMENT WEEK SITE TREATMENT*WEEK BASELINE / DDFM=KR;

REPEATED WEEK / SUBJECT=USUBJID TYPE=UN;

LSMEANS TREATMENT*WEEK / CL DIFF;

RUN;
```

A line plot showing the LS means and 95% CIs of the weekly mean NRS scores from Week 1 through Week 12 for each treatment group will be presented.

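### The weekly rescue-dose MMRM has no baseline term although rescue use is recorded daily before dosing, so precision is given up in a listed secondary endpoint

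*SAP*

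**What the plan says.** **Rescue dose.** SAP 3.2 lists rescue use, including the amount used, as a secondary endpoint. SAP 6.2.19 sums the tablets recorded in each week and multiplies by 500 mg. SAP 6.11.2.5 models that weekly dose over Weeks 1 to 12 with "study site, treatment group, week, and treatment-by-week interaction as terms in the model", and reports a treatment difference with a p-value at every week. No baseline rescue dose is defined.

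**What is collected before dosing.** Protocol 6.1 (Visit 1 and Screening Period) states: "Beginning at Week -1, DPN related pain intensity and rescue medication use will be recorded". The entry is made daily at bedtime on the handheld device. Protocol 8.7 and 15.1 require the last dose of a disallowed analgesic at least two weeks before randomisation, so the last seven pre-dose days fall after washout.

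**How the other visible models treat baseline.** For the primary endpoint, SAP 6.11.1.2 says: "The MMRM model will have site, treatment group, week, baseline NRS score, and treatment-by-week interaction as terms in the model". The DSIS model (6.11.2.1) and the QOL-DN model (6.11.2.4) adjust for their own baselines in the same way. Protocol 12.6.1.1 describes its MMRM as "including the baseline value of the response variable as a covariate".

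**PGI-C.** SAP 6.11.2.2 compares responder percentages by a CMH test and then adds an analysis of the score by the primary MMRM, "except with the exclusion of a baseline covariate".

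**The concern.** For rescue dose, the plan has a pre-treatment measurement of the outcome itself and does not use it. The last pre-dose week is collected on the same device, with the same question, after washout of disallowed analgesics. It is a natural candidate for a prognostic covariate. Without it, between-subject differences in habitual rescue use stay in the residual variance, and a chance difference between the arms in pre-dose use passes into the treatment estimate.

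The rescue comparison also helps in reading the pain result. The estimand in SAP 6.11.1.1 does not treat rescue use as an intercurrent event. A reader who wants to know whether unequal acetaminophen use could mask or explain a pain difference will look at this analysis. SAP section 9 lists the changes from the protocol analysis and gives no reason for leaving baseline out of this model.

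**Working it through.** **1. The plan's own figure.** SAP section 4 gives a difference of 0.73, SD 1.7, two-sided alpha 0.05, about 80% power and 15% dropout.

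- Per arm: 2 × (1.960 + 0.842)² × 1.7² / 0.73² = 85.1, rounded up to 86.
- With dropout: 86 / 0.85 = 101.2, rounded up to 102 per arm, so 204 in total.

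The stated N is reproduced exactly. It is built only on the primary NRS endpoint. The documents give no effect size, SD or power for rescue dose or PGI-C.

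**2. Gain from a baseline covariate.** Let r be the correlation between baseline and on-treatment rescue dose within site and treatment arm, since both are already in the model. The documents do not give r, so it is an assumption.

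- Residual variance factor = 1 − r²
- SE factor = √(1 − r²)
- Gain in effective sample size = 1/(1 − r²) − 1

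| Assumed r | Variance factor | SE factor | SE reduction | Effective-n gain |
|---|---|---|---|---|
| 0.1 | 0.99 | 0.995 | 0.5% | 1.0% |
| 0.2 | 0.96 | 0.980 | 2.0% | 4.2% |
| 0.3 | 0.91 | 0.954 | 4.6% | 9.9% |
| 0.4 | 0.84 | 0.917 | 8.3% | 19.0% |
| 0.5 | 0.75 | 0.866 | 13.4% | 33.3% |
| 0.6 | 0.64 | 0.800 | 20.0% | 56.2% |
| 0.7 | 0.51 | 0.714 | 28.6% | 96.1% |

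A single baseline term has one slope for all weeks, so at a given week the gain is at most about that shown for that week's r.

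**3. Cost of the covariate.** It uses about one degree of freedom. The approximate break-even is r = √(1/df): 0.082 at 150 df and 0.077 at 170 df, or about 0.08.

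**4. Chance imbalance.** With n per arm, one standard error of the baseline difference is √(2/n) baseline SDs. This moves the unadjusted treatment estimate by r × √(2/n) outcome SDs. The standard error of that estimate is √(2/n) outcome SDs. A one-SE imbalance in pre-dose rescue use therefore shifts the unadjusted result by r of its own standard error, for example half a standard error at r = 0.5.

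**5. PGI-C score model.** At an assumed r of 0.15 to 0.3 for baseline NRS, the SE factor is √(1 − 0.0225) = 0.989 to √(1 − 0.09) = 0.954. The saving is about 1% to 5%.

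**The case against.** **Size is assumed.** Nothing in the documents supports a particular correlation for rescue use, and at a low r the gain is negligible. This stands, and is why the size is given as a range.

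**Limited reach.** Randomisation protects the unadjusted comparison, so there is no bias on average and no inflation of type I error. Rescue dose is one of several rescue summaries. The protocol synopsis planned only descriptive summaries of rescue use, and SAP section 9 makes no multiplicity adjustment for secondary endpoints. All of this stands and keeps the point to one of efficiency.

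**More than one model term.** SAP 6.2.19 has no baseline rescue variable. The weekly-mean baseline in SAP 6.2.2 does not map directly onto an outcome built from weekly totals, and subjects without the covariate would drop out of the model. This also stands, so the fix includes a derivation and a minimum-entry rule.

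**PGI-C.** A reader might infer that the PGI-C exclusion is the same defect. The documents do not support that. SAP 6.2.20 describes PGI-C as a rating of change since the beginning of the study, so no baseline value can exist and the protocol's MMRM convention is not breached. The possible proxies have a narrowed range. PGI-S has four levels, with entry requiring "At least moderate pain intensity over the last week as assessed by PGI-S at Visit 1", and baseline NRS must fall within a masked eligibility algorithm. The score MMRM also only supplements the listed responder endpoint.

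**All other models.** A reader might infer that every other MMRM in the SAP adjusts for baseline. That cannot be checked, because the text of SAP 6.11.3 is not available. The comparison holds for the primary, DSIS and QOL-DN models.

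**Conclusion.** The point holds for the rescue-dose MMRM as a minor, inexpensive gain in efficiency. A baseline of the same measure is collected and not used, unlike in the other continuous-endpoint models that can be read. Under an assumed r of 0.3 to 0.7 the standard error of the rescue-dose difference would fall by about 5% to 29%. Any r above about 0.08 is enough to repay the lost degree of freedom. The analysis as written remains valid, and neither the primary analysis nor N = 204 is affected.

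A reader might express the gain as 272 to 400 subjects instead of 204, from 204/(1 − 0.5²) and 204/(1 − 0.7²). That overstates what the documents allow. The 204 was sized for the NRS endpoint and includes an allowance for dropout, no power is claimed for rescue dose, and both correlations are assumptions.

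**What to change.** 1. In SAP 6.2.19, define baseline rescue use as mean daily tablets over the available diary entries on Days -7 to -1. Add a minimum-entry rule, such as the 5 of 7 days that SAP 6.2.17.1 requires for baseline NRS. Pain and rescue use are both entered at bedtime in the same diary, so this rule should exclude few subjects beyond those who already lack a baseline NRS.
2. Add that variable as a covariate in the SAP 6.11.2.5 MMRM and record the change in SAP section 9.
3. Do both before unblinding, because a covariate added afterwards could look selective.
4. Optional and minor: add baseline NRS to the PGI-C score MMRM in SAP 6.11.2.2.

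The main change costs one derivation and one model term. It needs no new data.
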